**Table 2. Dose De-escalation Schema:**

Dose Level	Tretinoin Dose
-2	22.5 mg/m  /day, two divided doses
-1	33.75 mg/m  /day, two divided doses
0	45 mg/m  /day, two divided doses

Note: All treatment modifications must be expressed as a specific dose or amount rather than as a percentage of the starting or previous dose.

Tretinoin Dosing Should be *Delayed* if any of the following are present:

- Grade 3 drug-related creatinine, AST, ALT and/or Total Bilirubin abnormalities
- Grade 3 skin, drug-related adverse event
- Grade 3 drug-related laboratory abnormality, with the following exceptions:
  - Grade 3 lymphopenia
- Any adverse event, laboratory abnormality, or intercurrent illness which, in the judgment of the investigator, warrants delaying the dose of study medication.

Unacceptable Toxicity Warranting Drug *Discontinuation*:

- Any grade 4 adverse event will require *permanent discontinuation* with the following exceptions:
  - Grade 4 electrolyte abnormalities that are < 72 hours in duration
  - Grade 4 neutropenia or lymphopenia which are < 5 days in duration
  - Grade 4 elevation in cholesterol or triglycerides

The consideration to re-initiate study therapy under these exceptions will be made on a case by case basis after considering the overall benefit/risk profile and in consultation with the overall PI.

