## **5.5 Criteria for Taking a Participant Off Protocol Therapy**

Duration of therapy will depend on individual response, evidence of disease progression and tolerance. In the absence of treatment delays due to adverse event(s), treatment may continue until one of the following criteria applies:

- Disease progression
- Intercurrent illness that prevents further administration of treatment
- Unacceptable adverse event(s), *see Section 6.0*
- Participant demonstrates an inability or unwillingness to comply with the oral medication regimen and/or documentation requirements
- Participant decides to withdraw from the protocol therapy
- General or specific changes in the participant's condition render the participant unacceptable for further treatment in the judgment of the treating investigator
- Pregnancy

Participants will be removed from the protocol therapy when any of these criteria apply. The reason for removal from protocol therapy, and the date the participant was removed, must be documented in the case report form (CRF). Alternative care options will be discussed with the participant.

When a participant is removed from protocol therapy and/or is off of the study, the relevant Off-Treatment/Off-Study information will be updated in OnCore.

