If a patient experiences a Grade  $\geq 3$  toxicity that is felt to be related to tretinoin, then tretinoin will be held, until the toxicity has resolved to the Grade 1 level. At that time restart tretinoin at 25% dose reduction (or 33.75 mg/m^2/day divided twice daily) or Dose level -1 (see **Table 2**). Dosing of tretinoin should be as close as possible to 33.75 mg/m^2/day divided twice daily, i.e., rounded to the nearest 10 mg. Doses ending in  $\leq 5$  mg should be rounded down to the nearest 10 mg and doses  $> 5$  mg should be rounded up to the nearest 10 mg [e.g. 172 would round *down* to 170 mg; 176 would round *up* to 180 mg]. If necessary, the AM or morning dose may differ from the PM or afternoon dose to deliver a total daily dose as close as possible to 33.75 mg/m^2/day divided twice daily.

Recurrent episodes of Grade  $\geq 3$  toxicity will result in discontinuation of the tretinoin until the toxicity resolves to Grade  $\leq 1$ ; tretinoin can then be resumed with an additional 25% reduction (50% total dose reduction, Dose level -2) in the tretinoin dose (22.5 mg/m^2/day divided twice daily). Dosing of tretinoin should be as close as possible to 22.5 mg/m^2/day divided twice daily; rounded to the nearest 10 mg. Doses ending in  $\leq 5$  mg should be rounded down to the nearest 10 mg and doses  $> 5$  mg should be rounded up to the nearest 10 mg [e.g. 172 would round *down* to 170 mg; 176 would round *up* to 180 mg]. The higher dose of an uneven dose will be the AM or morning dose.

Patients experiencing Grade  $\geq 3$  toxicity attributable to tretinoin while on 22.5 mg/m^2/day of tretinoin should have tretinoin held until the toxicity resolves to Grade  $\leq 1$ . Tretinoin will then be resumed at the same 50% dose reduction (22.5 mg/m^2/day divided twice daily) while continuing to monitor for toxicity and holding doses as needed for Grade  $\geq 3$  toxicity. Please notify the study overall PI about patients experiencing Grade  $\geq 3$  toxicity while on 50% dose reduction. Patients with 3 episodes of Grade 3+ toxicity should be considered for therapy discontinuation in discussion with the overall PI.

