If patients whose doses are reduced by 25% (33.75 mg/m^2/day divided twice daily) or 50% (22.5 mg/m^2/day divided twice daily) tolerate the lower dose for 7 days without recurrence of the toxicity that led to dose adjustment, a dose escalation may be attempted. If the patient had been decreased to 50% dosing (22.5 mg/m^2/day divided twice daily) and tolerates an escalation to 75% dosing (33.75 mg/m^2/day divided twice daily) for an additional 7 days, another escalation back to 100% dosing (45 mg/m^2/day divided twice daily) may be attempted.

Tretinoin can be held on study up to 28 days or the length of one full cycle for toxicity reasons, at which point the patient should be removed considered for therapy discontinuation in discussion with the overall PI.

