#### Pseudotumor cerebri

Pseudotumor cerebri (PTC) must be confirmed by proper history, exam and other clinically relevant studies. Symptoms and/or signs of PTC include headache, papilledema, visual field defects (ocular or visual), and absence of focal neurological symptoms, except for occasional cranial nerve (CN) VI palsy. Cerebrospinal fluid should be evaluated and should be negative for signs of infection. However, lumbar puncture should be avoided while active coagulopathy is present. An opening pressure should be obtained; a pressure  $> 200$  mm water helps to establish the diagnosis of PTC. A CT or MRI of the brain (to evaluate for meningitis, intracranial bleed, intracranial thrombosis, etc.) should be performed and should be compatible with PTC. Neurological and ophthalmologic consultations should be obtained in order to assist in making the proper diagnosis. Carefully follow the visual field status of the patient. One should also strongly consider obtaining an MRI/MRV to exclude the possibility of a sagittal sinus thrombosis. Consider acetazolamide (Diamox) therapy and periodic lumbar puncture with therapeutic removal of cerebrospinal fluid as appropriate for age/size.

If PTC develops:

- Hold tretinoin until this toxicity improves to Grade 0 or 1 (“mild” headache)
- Restart tretinoin at 75% of the original dose (33.75 mg/m^2/day divided twice daily). If PTC reoccurs, hold tretinoin as above and then resume at 50% of original dose (22.5 mg/m^2/day divided twice daily)
- If the patient tolerates reduced dosing for more than 7 days, dose re-escalation can be attempted. Dose escalation from 50% (22.5 mg/m^2/day divided twice daily) to 75% (33.75 mg/m^2/day divided twice daily) to 100% (45 mg/m^2/day divided twice daily) at 7 day intervals may be attempted if clinically appropriate.

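### Protocol Section 6 both restarts and permanently stops tretinoin after a related Grade 4 event outside the three listed exceptions

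*Protocol*

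**What the plan says.** Protocol Section 6 contains three sets of rules that bear on a severe event.

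- **General rule (opening text of Section 6).** For a Grade ≥3 "toxicity that is felt to be related to tretinoin, then tretinoin will be held, until the toxicity has resolved to the Grade 1 level". The site is then told "At that time restart tretinoin at 25% dose reduction", giving 33.75 mg/m² per day. A recurrence leads to 22.5 mg/m² per day. After a further related Grade ≥3 event at that level, "Tretinoin will then be resumed at the same 50% dose reduction". The same text adds: "Patients with 3 episodes of Grade 3+ toxicity should be considered for therapy discontinuation in discussion with the overall PI". For patients on a reduced dose who "tolerate the lower dose for 7 days without recurrence of the toxicity that led to dose adjustment, a dose escalation may be attempted", with a path back to 45 mg/m² per day.
- **Pseudotumor cerebri.** The drug is held until the event improves to Grade 0 or 1, then "Restart tretinoin at 75% of the original dose", with 50% on recurrence and re-escalation possible. No grade at onset is named.
- **Lists below Table 2.** The graded entries in the delay list name Grade 3 only. The discontinuation list, headed as unacceptable toxicity, reads "Any grade 4 adverse event will require *permanent discontinuation* with the following exceptions". The exceptions are electrolyte abnormalities under 72 hours, neutropenia or lymphopenia under 5 days, and raised cholesterol or triglycerides. For these, restarting is an individual decision taken with the overall PI.

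Section 5.5 names unacceptable adverse events as a reason to stop, refers to Section 6 for them, and says "Participants will be removed from the protocol therapy when any of these criteria apply". The SAP does not address dose modification.

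**The concern.** The threshold in the general rule has no upper limit, so it takes in Grade 4. Its restart step is an instruction, not an option. The discontinuation list is equally firm in the other direction. Staff who follow the general rule as written would give tretinoin again to a patient whom the list takes off the drug for good, and could later return that patient to full dose.

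The example is not remote from the protocol's own expectations. Section 6 names raised AST and ALT among the toxicities commonly seen with tretinoin, although it does not say at what grade. Cohort 2 was added to learn whether continuous dosing is safe and tolerable in 6 patients (Section 13), so the stopping rule ought to have one meaning there.

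**Working it through.** No statistical figure is involved. The check is whether the rules can be followed together for each kind of event.

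**Scope of each rule.** The general rule applies to events that are related to tretinoin and are Grade 3 or higher. The discontinuation list applies to any Grade 4 event, whatever its attribution, apart from the three exceptions. They overlap in events that are related, Grade 4 and not excepted.

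**Doses.** Level -1 is 0.75 × 45 = 33.75 mg/m² per day and level -2 is 0.50 × 45 = 22.5 mg/m² per day, as in Table 2. Under permanent discontinuation the dose is 0.

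| Event | Hold-and-restart text | Lists below Table 2 | Can both be followed? |
|---|---|---|---|
| Related Grade 3 AST or ALT rise | Hold, restart at 33.75 | Delay | Yes |
| Related Grade 4, excepted | Hold, restart at reduced dose | Restart decided individually with the overall PI | Yes: the list decides whether, the general rule supplies the dose |
| Related Grade 4, not excepted (such as an ALT rise) | Hold, restart at 33.75 | Permanent discontinuation | **No** |
| Unrelated Grade 4, not excepted | Does not apply | Permanent discontinuation | Yes |
| Pseudotumor cerebri below Grade 4 | Hold, restart at 33.75 | No discontinuation required | Yes |
| Pseudotumor cerebri, if Grade 4 | Hold, restart at 33.75 (no grade limit stated) | Permanent discontinuation | **No** |

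The third row is an explicit conflict, because Grade ≥3 includes Grade 4. The last row is implicit: it arises from silence about grade, and only if an event of that grade occurs.

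**Is precedence stated anywhere?** Section 5.5 makes removal mandatory for unacceptable adverse events but sends the reader to Section 6, which holds both rules. The heading of the discontinuation list matches the term in Section 5.5, which points to that list. Neither the general rule nor the pseudotumor cerebri text excludes Grade 4 or refers to the list. The general rule also uses the word discontinuation for a temporary stop after a recurrence, so the word alone does not separate the two rules. The three-episode sentence counts Grade 3+ events and only asks that stopping be considered, without limiting the Grade 4 events in that count to the excepted ones.

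**The case against.** The best defence is that the protocol can be read coherently. Removal under Section 5.5 is mandatory. Section 6 has one list headed as unacceptable toxicity. The graded delay entries stop at Grade 3, so Grade 4 looks like a separate tier. The Grade ≥3 wording also has a legitimate use, since excepted Grade 4 events may restart and need a dose. On this view only a cross-reference is missing.

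There are safeguards too. Life-threatening complications go to the PI at once (Sections 5.7 and 7.3.1). Grade 4 events are generally reportable within 5 calendar days (Section 7.4). The DSMC reviews toxicity (Section 12.2). Sections 4.3 and 12.3 mark outside sites and multi-center guidelines as not applicable, so few teams could diverge.

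Much of this stands. The discontinuation list is probably meant to govern, and the safeguards lower the chance that a wrong restart goes unnoticed. But none of them says which rule prevails, and the general rule comes first, gives exact doses and reads as complete. The argument that the specific rule overrides the general one also works the wrong way for pseudotumor cerebri, where the event-specific text is the one that restarts the drug.

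A reader might infer more than the documents support:

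- *That the protocol directs a restart after Grade 4 pseudotumor cerebri.* It is silent on grade. What Grade 4 would mean for this event depends on CTCAE v5.0, which is not reproduced in the documents.
- *That a number of patients or a quantity of drug is at stake.* No Grade 4 frequency is given, and Section 13 reports no worrying serious adverse events in Cohort 1. Any total would be multiplication for a hypothetical patient.
- *That the Grade 3 lymphopenia exemption in the delay list is void because the general rule lacks it.* An express exception can be read as qualifying a general rule. This is an alignment point, not a contradiction.

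**Conclusion.** The point holds. For a tretinoin-related Grade 4 event outside the three exceptions, Section 6 says both to restart at 33.75 mg/m² per day and never to restart. The same gap exists for pseudotumor cerebri only if an event reaches Grade 4. The sponsor should correct it, because the possible error is re-exposure after a severe related event.

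Its reach is limited. A reader might infer that the efficacy results are compromised, but the documents do not support that: the sample size, the endpoints and the response analysis, which takes all eligible patients who begin treatment, do not depend on which rule is applied. No count of affected patients is claimed. The conclusion rests on reading Grade ≥3 and Grade 3+ literally and on the absence of any precedence statement in Sections 5.5 and 6.

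**What to change.** In the general rule of Section 6, state that:

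- the hold-and-restart steps apply to related Grade 3 toxicity, and to the three excepted kinds of Grade 4 event once the overall PI agrees to re-initiate, at the dose levels given in that text;
- every other Grade 4 event means permanent discontinuation under the list below Table 2, which takes precedence;
- the three-episode sentence counts only Grade 3 and excepted Grade 4 events.

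Add the same precedence sentence before the restart instruction for pseudotumor cerebri. If the sponsor does intend restart after Grade 4 hepatic events or Grade 4 pseudotumor cerebri, add them to the exceptions below Table 2 instead.

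Simply limiting the general rule to Grade 3 would not be enough, because excepted Grade 4 events would then have no restart dose.

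Optionally, carry the Grade 3 lymphopenia exemption from the delay list into the general rule.

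The cost is a few sentences in Section 6, with no change to sample size, endpoints, visits or analyses.

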## 7. ADVERSE EVENTS: LIST AND REPORTING REQUIREMENTS

Adverse event (AE) monitoring and reporting is a routine part of every clinical trial. The following list of reported and/or potential AEs (Section 7.1) and the characteristics of an observed AE (Section 7.2) will determine whether the event requires expedited reporting **in addition** to routine reporting.

### 7.1 Expected Toxicities

Virtually all patients treated with tretinoin experience some drug related toxicity, especially headache, fever, weakness, and fatigue. These adverse effects are seldom permanent or irreversible nor do they usually require interruption of therapy. Please see the Package Insert at the bottom of the protocol document for details.

### 7.2 Adverse Event Characteristics

- **CTCAE term (AE description) and grade:** The descriptions and grading scales found in the revised NCI Common Terminology Criteria for Adverse Events (CTCAE) version 5.0 will be utilized for AE reporting. All appropriate treatment areas should have access to a

copy of the CTCAE version 5.0. A copy of the CTCAE version 5.0 can be downloaded from the CTEP web site [http://ctep.cancer.gov/protocolDevelopment/electronic\\_applications/ctc.htm](http://ctep.cancer.gov/protocolDevelopment/electronic_applications/ctc.htm).

- **For expedited reporting purposes only:**
  - AEs for the agent(s) that are listed above should be reported only if the adverse event varies in nature, intensity or frequency from the expected toxicity information which is provided.
- **Attribution** of the AE:
  - Definite – The AE *is clearly related* to the study treatment.
  - Probable – The AE *is likely related* to the study treatment.
  - Possible – The AE *may be related* to the study treatment.
  - Unlikely – The AE *is doubtfully related* to the study treatment.
  - Unrelated – The AE *is clearly NOT related* to the study treatment.

### 7.3 Adverse Event Reporting

7.3.1 In the event of an unanticipated problem or life-threatening complications treating investigators must immediately notify the PI.

7.3.2 PI **must** report any adverse event (AE) that occurs after the initial dose of study treatment, during treatment, or within 30 days of the last dose of treatment on the local institutional SAE form.

7.3.3 Serious Adverse Events

7.3.3.1 Definition

A **Serious Adverse Event (SAE)** is any untoward medical occurrence that at any dose:

- Results in death
- Is life-threatening (defined as an event in which the participant was at risk of death at the time of the event; it does not refer to an event which hypothetically might have caused death if it were more severe)
- Requires inpatient hospitalization or causes prolongation of existing hospitalization (see **NOTE** below)
- Results in persistent or significant disability/incapacity
- Is a congenital anomaly/birth defect
- Is an important medical event (defined as a medical event(s) that may not be immediately life-threatening or result in death or hospitalization but, based upon appropriate medical and scientific judgment, may jeopardize the subject or may require intervention [eg, medical, surgical] to prevent one of the other serious outcomes listed in the definition above.) Examples of such events include, but are not limited to, intensive treatment in an emergency room or at

home for allergic bronchospasm; blood dyscrasias or convulsions that do not result in hospitalization.)

- Suspected transmission of an infectious agent (eg, pathogenic or nonpathogenic) via the study drug is an SAE.

Although pregnancy, overdose, potential drug-induced liver injury (DILI), and cancer are not always serious by regulatory definition, these events must be handled as SAEs.

Any component of a study endpoint that is considered related to study therapy should be reported as an SAE (eg, death is an endpoint, if death occurred due to anaphylaxis, anaphylaxis must be reported).

### 7.3.3.2 Reporting SAEs

Following the subject’s written consent to participate in the study, all SAEs, whether related or not related to study drug, must be collected, including those thought to be associated with protocol-specified procedures. All SAEs must be collected that occur within 100 days of discontinuation of dosing. All SAEs should be followed to resolution or stabilization.

## 7.4 DF/HCC Adverse Event Reporting Guidelines

Investigative sites within DF/HCC will report AEs directly to the DFCI Office for Human Research Studies (OHRS) per the DFCI IRB reporting policy.

Other investigative sites will report AEs to their respective IRB according to the local IRB’s policies and procedures in reporting adverse events. A copy of the submitted institutional AE form should be forwarded to the Overall PI within the timeframes detailed in the table below:

Attribution	DF/HCC Reportable Adverse Events(AEs)				
	Gr. 2 & 3 AE Expected	Gr. 2 & 3 AE Unexpected	Gr. 4 AE Expected	Gr. 4 AE Unexpected	Gr. 5 AE Expected or Unexpected
Unrelated Unlikely	Not required	Not required	5 calendar days #	5 calendar days	24 hours*
Possible Probable Definite	Not required	5 calendar days	5 calendar days #	5 calendar days	24 hours*
# If listed in protocol as expected and not requiring expedited reporting, event does not need to be reported.					
* For participants enrolled and actively participating in the study or for AEs occurring within 30 days of the last intervention, the AE should be reported within 1 business day of learning of the event.					

The Overall PI will submit AE reports from outside institutions to the DFCI OHRS according to DFCI IRB policies and procedures in reporting adverse events.

## 7.5 Reporting to the Food and Drug Administration (FDA)

The PI, as study sponsor, will be responsible for all communications with the FDA. The PI will report to the FDA, regardless of the site of occurrence, any serious adverse event that meets the FDA's criteria for expedited reporting following the reporting requirements and timelines set by the FDA.

#### **7.6 Reporting to Hospital Risk Management**

PI will report to local Risk Management office any participant safety reports, sentinel events or unanticipated problems that require reporting per institutional policy.

#### **7.7 Routine Adverse Event Reporting**

All Adverse Events **must** be reported in routine study data submissions to the PI on the toxicity case report forms. **AEs reported through expedited processes (e.g., reported to the IRB, FDA, etc.) must also be reported in routine study data submissions.**

### **8. PHARMACEUTICAL INFORMATION**

Information in *Section 8* is based on the Teva Pharmaceuticals USA, Inc. package insert.

[figure not shown]
#### **8.1 Study Agent: Tretinoin**

All-trans retinoic acid (ATRA); generic name: *Tretinoin*; trade name: *Vesanoid*®

##### **8.1.1 Description**

Tretinoin, USP is a retinoid that induces maturation of acute promyelocytic leukemia (APL) cells in culture. It is available in a 10 mg gelatin capsule for oral administration. Each capsule contains the following inactive ingredients: butylated hydroxyanisole, edetate disodium, gelatin, hydrogenated vegetable oil, polysorbate 80, soybean oil, vitamin E, and white wax (beeswax). The ingredients in the capsule shell include black iron oxide, red iron oxide, titanium dioxide and yellow iron oxide. The ingredients in the edible imprinting ink include D&C yellow no. 10 aluminum lake, FD&C blue no. 1 aluminum lake, FD&C blue no. 2 aluminum lake, FD&C red no. 40 aluminum lake, iron oxide black, propylene glycol and shellac glaze.

Chemically, tretinoin, USP is all-*trans* retinoic acid and is related to retinol (Vitamin A) and has the following chemical name: 3,7-Dimethyl-9-(2,6,6-trimethyl-1-cyclohexen-1-yl)-2,4,6,8-nonatetraenoic acid. It is a yellow to light orange crystalline powder, and has the following structural formula:

